#### 15.2.2. PRIMARY END POINT HYPOTHESIS ANALYSIS

The primary endpoint is the bowel cleansing level, as determined by BBPS scoring index, assessed in total and by segment (cecum, ascending, transverse, descending/sigmoid, and rectum).

The primary statistical hypothesis is that the rate of adequate cleansing level (i.e., BBPS>1) post MCS procedure will significantly improve as compared to the rate of adequate cleansing level pre procedure (prior the MCS use) , assuming 60% chance for improvement (P01).

The primary performance assessment will be based on data from all colon segments observed during the colonoscopy procedure.

Chi-square or Fisher’s exact test, as appropriate, will be performed in order to compare proportions of good or excellent cleansing level (i.e., BBPS>1) pre and post MCS procedure.

In addition, frequency counts, percentages, and 95% confidence intervals will be provided.

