#### 14.1.1. PRE- PROCEDURE CLEANSING PER SUBJECT

Evaluating the cleansing (preparation) rate while inserting the device, prior to the cleaning procedure, for the entire colon.

This measurement will serve as the subjects' baseline condition with regards to colon cleansing.

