## 15. STATISTICAL CONSIDERATIONS

### 15.1. DETERMINATION OF SAMPLE SIZE

The primary objective of the study is to evaluate the effectiveness of MCS in cleansing a poorly prepared colon.

Based on previous study data (pre-clinical and clinical), 36% and 96% success rates of good/excellent cleansing levels are have been found for pre procedure and post procedure, respectively.

A sample size of 47 patients is required as per McNemar test to determine that the paired discordant proportion are significantly different under the followings assumptions:

Probability of Type I Error ( $\alpha$ ) = 0.05

Power ( $1 - \beta$ ) = 0.8

Proportion switching from + to - = 0

Proportion switching from - to + = 0.6

Sample size required (number of pairs) = 11

This pilot study will include 3 sites (i.e., 2 sites in NL and 1 site in Germany). As per McNemar sample size calculation 11 subjects will be recruited per site.

Adding 10% of drop out (i.e. 4 cases) and additional 9 cases (The first 3 subjects of each physician) that will be excluded from the secondary analysis in order to compensate the system operation learning curve.

The overall sample size is as follows:

3 subjects per site for training - overall 9 subjects

11 subjects per site - overall 33 subjects

Addition of 10% of withdrawn subjects - 4 subjects

Therefore , up to 47 subjects (15-16 subjects per site) are planned to be enrolled to this study.

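### The primary pre/post comparison uses the same subjects twice, but the plan tests it with chi-square or Fisher's exact test instead of the McNemar test on which the study was sized

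*Combined protocol and SAP*

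**What the plan says.** Section 10 describes a single-arm, open study. Section 12.5 has each colon segment scored on the BBPS during insertion, before cleansing, and again during withdrawal, after cleansing. Section 14.1.1 says of the first score: "This measurement will serve as the subjects' baseline condition with regards to colon cleansing".

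Section 15.1 bases the sample size on a paired test: "A sample size of 47 patients is required as per McNemar test to determine that the paired discordant proportion are significantly different". Its inputs are alpha 0.05, power 0.8, "Proportion switching from + to - = 0" and 0.6 switching the other way. The result is 11 pairs, which the plan then applies to each of three sites to give 33 subjects, before training cases and dropouts are added.

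Section 15.2.2 states the primary hypothesis with the same paired parameter, P01 = 60%. The test it names is different: "Chi-square or Fisher’s exact test, as appropriate, will be performed in order to compare proportions of good or excellent cleansing level", pre against post. It also promises counts, percentages and 95% confidence intervals, without saying which quantity the intervals are for. McNemar's test, or any other paired method, appears in no analysis section.

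**The concern.** Chi-square and Fisher's exact test compare two independent groups. Here there is one group measured twice, so a table of pre and post totals counts 33 subjects as 66 observations and discards who changed.

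The direction of the error depends on the within-subject correlation. If subjects who were adequate before stay adequate after, as the plan assumes, the unpaired p-value is too large and power is lost. If many subjects switched in both directions, the unpaired test could reject more often than 5% under the null. In neither case does the nominal 5% apply, and the 80% power in section 15.1 was not calculated for the test that would be run.

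This is the only test specified for the only primary endpoint. The phrase 'as appropriate' also leaves the choice between two tests open. Under section 15.2, a later switch to a paired test would count as a departure from the plan, reported in addition to the planned analysis.

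**Working it through.** **Inputs.** From section 15.1: alpha 0.05; power 0.80; p01 (inadequate to adequate) = 0.6; p10 (adequate to inadequate) = 0; pre and post rates 0.36 and 0.96; 33 evaluable subjects. Sidedness is not stated. I take it as two-sided, because that reproduces the plan's figure.

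**1. The plan's own sample size.** McNemar, normal approximation:

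n = [z(0.975)·√(p01 + p10) + z(0.80)·√((p01 + p10) − (p01 − p10)²)]² / (p01 − p10)²

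= [1.960·√0.6 + 0.842·√(0.6 − 0.36)]² / 0.36 = [1.518 + 0.412]² / 0.36 = 10.35, rounded up to **11**.

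This matches the plan. The one-sided version gives 8. An unpaired two-proportion calculation for 0.36 against 0.96 gives 9 per group, or 12 with continuity correction. The 11 is therefore a paired figure.

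**2. What the tests do to the same data.** Take 33 subjects, 12 adequate before (36%), b improving and none worsening. Exact McNemar gives p = 2 × 0.5^b. Chi-square (uncorrected) and Fisher use the totals 12/33 against (12 + b)/33. For b = 6, chi-square is 66 × (12×15 − 21×18)² / (33 × 33 × 30 × 36) = 2.20, p = 0.138.

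| Improved (b) | Exact McNemar p | Chi-square p | Fisher p |
|---|---|---|---|
| 5 | 0.063 | 0.215 | 0.321 |
| 6 | 0.031 | 0.138 | 0.216 |
| 7 | 0.016 | 0.084 | 0.138 |
| 8 | 0.008 | 0.049 | 0.084 |
| 9 | 0.004 | 0.027 | 0.048 |

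The conclusions differ for b = 6, 7 or 8. At b = 8 the two tests that the plan names disagree with each other.

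**3. Power with 33 subjects** (pre rate 0.36, p10 = 0, exact enumeration of the paired table). The 0.60 gain is the plan's; the smaller gains are assumptions chosen to show the range.

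| True gain p01 | Exact McNemar | Chi-square | Fisher |
|---|---|---|---|
| 0.20 | 67% | 34% | 20% |
| 0.25 | 87% | 61% | 45% |
| 0.30 | 96% | 82% | 70% |
| 0.60 (planned) | >99.9% | >99.9% | >99.9% |

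**4. True type I error with 33 subjects** (both rates 0.36; the switching rates are assumptions).

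| p01 = p10 | Chi-square | Fisher | Exact McNemar |
|---|---|---|---|
| 0.10 | 0.4% | 0.1% | 1.5% |
| 0.15 | 1.8% | 0.7% | 2.2% |
| 0.20 | 4.0% | 1.9% | 2.6% |
| 0.30 | 9.3% | 5.6% | 3.0% |

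Chi-square passes 5% at about p01 = p10 = 0.22. Exact McNemar stays below 5% at every rate shown.

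**5. Interval for the difference, if one is given** (b = 8, difference 8/33 = 24.2 points).

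- Paired: SE = √(b − b²/n)/n = √(8 − 64/33)/33 = 0.0746; half-width 1.96 × 0.0746 = 14.6 points.
- Treated as independent: SE = √[(12/33 × 21/33 + 20/33 × 13/33)/33] = 0.1194; half-width 23.4 points.

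**The case against.** The strongest reply is that nothing would change in practice. The plan expects 36% to rise to 96%, and sections 4.4 and 4.7 report 30% rising to 93% with the same preparation. About 20 of 33 subjects should improve (0.6 × 33 = 19.8), while the tests part company only at 6 to 8. At p01 = 0.60 the chance of 8 or fewer is about 3 in 100,000. With p10 = 0 the unpaired test is conservative, so a significant result would understate the evidence. The 9.3% error rate needs 30% of subjects to become inadequate after cleansing, which the plan assumes does not happen. All of this stands, and it limits the practical harm.

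A second reply is that the paired intent is visible: section 15.2.2 uses P01, and McNemar's statistic is itself a chi-square. This does not rescue the sentence. Fisher's test as the small-sample alternative belongs to independent groups; the exact form of McNemar is a binomial test on the discordant pairs.

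Third, section 15.2.2 does not say that its intervals are for the pre/post difference, and separate intervals for each percentage would be sound. That is fair. The comparison of widths applies only if an unpaired interval for the difference is reported.

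Fourth, the exact test is more demanding than the formula behind the 11 pairs: with 11 pairs its power is 75.4%, not 80%. That would matter only if one site were analysed alone. With 33 pairs it exceeds 99.9%.

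**Conclusion.** The concern holds. Read as written, section 15.2.2 applies an independent-groups test to matched pairs and does not match the McNemar calculation in section 15.1. The nominal 5% level and the stated power do not belong to the named tests.

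The practical effect depends on the true gain. At the planned 60 points it is negligible. At gains of 20 to 30 points with no worsening, power is lower than with exact McNemar by 14 to 33 percentage points for chi-square and by 26 to 47 for Fisher. Under the plan's assumption of no worsening the error is conservative; inflation above 5% needs heavy two-way switching. These figures assume 33 evaluable subjects, a pre-procedure rate of 36%, two-sided testing and uncorrected chi-square.

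It should be corrected before analysis, because the test of the only primary hypothesis must be valid whatever effect is observed.

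**What to change.** In section 15.2.2, replace the chi-square/Fisher sentence with:

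> The pre and post adequate-cleansing rates will be compared by a two-sided exact McNemar test at alpha 0.05, and the paired difference will be given with a 95% confidence interval for matched proportions.

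This also settles the sidedness, which the plan leaves open. If the by-segment results in the same section are to be tested as well, the same paired method should be named for them. The cost is one sentence of wording: no extra data, no extra subjects and no change to the 33 evaluable pairs.

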#### 15.2.3. SECONDARY SAFETY ANALYSIS

The secondary endpoint is to evaluate the Device related adverse event and the overall adverse events rate.

The safety analysis set will consist of all subjects who were enrolled into the study.

Individual listings of adverse events including type of device, adverse events (reported term), seriousness, duration, relationship to the study device, severity and the adverse events outcome will be provided for the total population and per population group.

AEs will be summarized using frequency counts and percentages.

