### **12.2. SUBJECT ASSIGNMENT**

The study-center will be identified by a single digit number (e.g., 01). The center will assign to enrolled subjects a number in sequence to coincide with the sequence of enrollment. Therefore each subject will be unequivocally identified by a 2-digit center identifier followed by a three digit subject identifier (eg 01-001). Once enrolled at the eligibility assessment visit, the subject will be requested to follow study procedures.

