### **Visit 1- Screening visit**

Subjects will be assessed for eligibility to participate based on the inclusion and exclusion criteria.

When it has been established that the subject is potentially eligible , written informed consent will be obtained during the visit. The subject will sign and date the consent form. The Investigator will also sign and date the consent form. The original of the informed consent form will be retained with the subject records and a copy will be provided to the subject.

The subject will be recorded on the Subject Enrollment and Visit Log and his/her eligibility will be confirmed.

After eligibility is confirmed, the subject's baseline condition will be assessed and entered to the CRF to include: subject population group, age, gender, race, height, weight, medical records/history and reason for referral.

The colonoscopy procedure will be scheduled to be at least 2 days ahead but no later than 30 days.

In the event that the screening and eligibility assessment takes place more than 30 days prior to the planned procedure date, the investigator should contact the subject prior to the procedure date to assure there is no change in the subject's medical condition.

Subjects will be instructed regarding the preparation regime and will be given the diaries which are needed to be filled out during the preparation phase.

The Physician will instruct the subject to bring the diaries to the scheduled colonoscopy.

Subjects who were found to be not eligible for the study following signature of the Informed Consent Form , will be withdrawn from the study. The following procedures will not be performed in these

subjects, the Subject Enrollment and Visit Log will be completed and the subject eligibility section in visit 1 as well as a "Study Completion" form will be completed in the CRF.

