## **12.5. COLONOSCOPY PROCEDURE (VISIT 2)**

### Pre-Examination Procedures

- Verify eligibility checked and informed consent was obtained after explaining all risks, benefits, and alternatives to the candidate.
- Verify that the research assistant has collected completed diaries from the subject.
- Verify all background/clinical information, demographic and medical history was documented
  - Note: Subjects that did not take the bowel preparation or failed to complete the bowel preparation will not undergo the procedure and will be excluded from the study.
- Verify all connections and assemblies are properly attached (see Instructions for Use “Setup and Interconnections” section and sections 5.4 and 5.5. in this protocol )
- Verify device works properly (see Instructions for Use “System Operation” section and sections 5.4 and 5.5. in this protocol)
- Place and prepare the subject for the procedure as per standard colonoscopy.
- Perform a digital rectal exam as per standard colonoscopy , evaluate the adequate level of the preparation and start the colonoscopy procedure as per standard of care.

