## **13. STUDY COMPLETION PROCEDURES**

### **13.1. SUBJECT COMPLETION OF STUDY**

Subjects are considered to have completed the study if they have completed all study requirements up to the 14 day follow up call. All subjects enrolled in the clinical investigation (including those withdrawn and those who were screened failure) shall be accounted for and documented.

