### **13.2. SUBJECT WITHDRAWAL**

Subjects will be withdrawn from the study if one of the following occurs;

- The subject voluntarily discontinues his or her participation in the study.
- Continuation of the course of the study would jeopardize the subject's health and/or welfare (at the discretion of the Investigator)
- There is a concurrent illness (unrelated to treatment) that prevents the subject from complying with the study requirements
- The subject is unwilling or unable to comply with the protocol
- The subject was found to be not-eligible following signature of the Informed Consent Form .

The reasons for the subject's withdrawal from the study must be recorded in the subject's CRF and captured on the Subject Enrollment and Visit Log. All withdrawn subjects having performed the colonoscopy procedure with MCS, will be followed up to 14 days post procedure to verify that there have been no changes in their well-being for the entire period of the study.

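### The device-related adverse event rate is taken over all enrolled subjects, so anyone enrolled who never receives the MCS can only lower it

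*Combined protocol and SAP*

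**What the plan says.** Section 15.2.3 states the safety endpoint as two rates: "The secondary endpoint is to evaluate the Device related adverse event and the overall adverse events rate". It names one population for both: "The safety analysis set will consist of all subjects who were enrolled into the study". The summary is simple: "AEs will be summarized using frequency counts and percentages". No denominator of exposed subjects is given there or elsewhere.

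Enrolment comes before exposure. Section 12.2 places it at the first visit: "Once enrolled at the eligibility assessment visit, the subject will be requested to follow study procedures". Section 12.3 (Visit 1) sets the gap: "The colonoscopy procedure will be scheduled to be at least 2 days ahead but no later than 30 days". It also provides for screening more than 30 days ahead.

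Three groups can fall between enrolment and exposure:

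- **Withdrawals before Visit 2.** Section 13.2 allows withdrawal at any time. It also lists this reason: "The subject was found to be not-eligible following signature of the Informed Consent Form".
- **Unprepared subjects.** Section 12.5 says that those who did not take the preparation or "failed to complete the bowel preparation will not undergo the procedure and will be excluded from the study".
- **Screen failures.** Section 13.1 counts them when it describes who must be accounted for: "All subjects enrolled in the clinical investigation (including those withdrawn and those who were screened failure". Section 11.1, by contrast, speaks of up to 47 eligible subjects being enrolled.

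Sections 15.2.1 and 15.5 remove withdrawals and unprepared subjects from the performance analysis. Section 15.2.3 has no matching rule for safety.

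**The concern.** A subject in whom the MCS was never used cannot have an event caused by it. Counted in the safety set, that subject raises the denominator of the device-related rate and leaves the numerator alone. The error runs in one direction only, toward the device.

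Safety is the only secondary objective (Section 6.2). Section 14.2 sets the MCS-related severe event rate beside a figure of about 0.35% for major complications of routine colonoscopy. That reference describes people who had the procedure, so the MCS rate should describe people who had it too. The same holds for procedure-related events, since Section 4.2 says that MCS complications cannot be told apart from those of the colonoscopy.

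Follow-up adds a smaller problem. Section 13.2 promises 14 days of follow-up to withdrawn subjects only if they had the MCS procedure. Unexposed subjects would therefore be counted without assured AE ascertainment.

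**Working it through.** **1. The plan's own denominator.** Section 15.1 gives α = 0.05, power 0.80, and switching proportions 0.6 and 0. With a two-sided α (sidedness is not stated) and pd = d = 0.6, the McNemar normal-approximation formula is

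n = [z(0.975)·√pd + z(0.80)·√(pd − d²)]² / d²
= [1.960·√0.6 + 0.842·√0.24]² / 0.36 = 10.35, rounded up to 11 pairs per site.

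Three sites give 33, and training subjects add 9, making 42. Allowing for 10% loss, 42/0.9 = 46.7, which rounds up to 47. (The parts as listed, 33 + 9 + 4, sum to 46. This does not affect the present point.) So N = 47 is the planned maximum enrolment.

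**2. The dilution.** Let u be the number enrolled but never exposed, and x the number of exposed subjects with a device-related AE.

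- Rate as planned: x/47
- Rate in exposed subjects: x/(47 − u)
- Ratio of the first to the second: (47 − u)/47, whatever the value of x

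**3. The value of u.** The documents do not give it. Section 15.1 allows for 4 withdrawals without saying whether they precede the procedure, so that allowance supports any u from 0 to 4. Values above 4 are assumptions, included to show the range. Neither x nor any AE rate is stated; the event counts are illustrative.

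| u | Exposed | Ratio | 1 event: planned vs exposed | 3 events: planned vs exposed |
|---|---|---|---|---|
| 0 | 47 | 1.000 | 2.13% vs 2.13% | 6.38% vs 6.38% |
| 2 | 45 | 0.957 | 2.13% vs 2.22% | 6.38% vs 6.67% |
| 4 | 43 | 0.915 | 2.13% vs 2.33% | 6.38% vs 6.98% |
| 8 (assumed) | 39 | 0.830 | 2.13% vs 2.56% | 6.38% vs 7.69% |
| 10 (assumed) | 37 | 0.787 | 2.13% vs 2.70% | 6.38% vs 8.11% |

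At u = 4 the relative understatement is 1 − 43/47 = 8.5%. That is 0.2 percentage points for one event and 0.6 for three.

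**4. The comparison with 0.35%.** No events give 0% on either denominator. One event gives 2.1% on 47 and 2.3% on 43, both well above 0.35%. The choice of denominator shifts the reported figure but does not move it across the reference.

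**The case against.** The strongest reply is that the set may be less diluted than it looks, and that little depends on it. Much of this stands.

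- **Who is enrolled.** A reader might infer that every screen failure and every unprepared subject is in the denominator. The documents do not establish that. Section 11.1 ties enrolment to eligible subjects, Section 12.5 says that unprepared subjects leave the study, and the sentence in Section 13.1 concerns subject accounting and does not define an analysis set. These sections conflict with one another and need reconciling. Eligible subjects who withdraw before Visit 2 remain enrolled on any reading.
- **The 4 withdrawals.** It is tempting to treat them as the plan's own count of untreated subjects. Section 15.1 gives no timing, and Section 13.2 expressly provides for withdrawal after the MCS procedure. Four is the most that the allowance can supply, and zero is possible.
- **Uncertainty.** A reader might also conclude that the plan understates the uncertainty of the AE rates. No interval is planned for them; the 95% intervals are for cleansing (Section 15.2.2) and cecal intubation (Section 15.2.4). A reader who computed the exact two-sided 95% upper limit for zero events, 1 − 0.025^(1/n), would get 7.5% at 47 and 8.2% at 43, but neither is a planned output.
- **All enrolled as a safety set.** It would be wrong to reject it outright. The limited bisacodyl preparation is part of the study and carries its own listed risks (Sections 4.2 and 4.5), so all enrolled is defensible for the overall AE rate.
- **Consequence.** There is no safety test or success threshold. The listings of AEs (Section 15.2.3) and of withdrawals and failures (Section 15.2.1) would let a careful reader largely rebuild the exposed denominator.

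None of this supplies a denominator of exposed subjects for the device-related rate, which is what the plan lacks.

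**Conclusion.** The point holds for the device- and procedure-related AE rates, and only for those. As written, Section 15.2.3 divides device-related events by all enrolled subjects, and the protocol provides ways to be enrolled and never receive the MCS. The direction is fixed, toward the device.

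The size is modest: at most an 8.5% relative understatement if all 4 planned withdrawals precede insertion, about 21% if 10 of 47 were unexposed (an assumption without a source in the documents), and none if every enrolled subject is exposed or no device-related event occurs. It would not change a decision rule, because there is none for safety. It is still worth settling before the data are seen, since the unclear meaning of enrolled leaves the denominator open to choice afterwards.

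**What to change.** In Section 15.2.3:

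1. Report device- and procedure-related AE rates over all subjects in whom MCS insertion was attempted. Include the learning-curve subjects (Section 14 already keeps them for safety), technical failures and incomplete procedures.
2. Keep all enrolled subjects for the overall AE rate and for the individual listings.
3. State whether screen failures and unprepared subjects count as enrolled, and bring Sections 11.1, 12.5, 13.1 and 15.2.3 into line.
4. Use the attempted-insertion set for the comparison with about 0.35% in Section 14.2.

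The cost is a few sentences. No extra subjects or visits are needed: the procedure is already documented in the CRF, and Section 26.2 already links each dispensed add-on to a subject number. The downside for the sponsor is that the device-related rates become slightly less favourable.
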